
Study protocol

This study will be a prospective cohort model comparing between the efficacy of different MRI sequences in visualization of the facial nerves.

Patient recruitment

Inclusion: Consecutive patients with parotid tumour diagnosed on other imaging modalities (such as ultrasonography or computed tomography), with or without cytological diagnosis from fine needle aspiration, will be recruited from the ear, nose and throat specialty clinic.

Exclusion:

- Patients who are contraindicated to magnetic resonance imaging (such as due to underlying MRI incompatible metallic implants)
- Patient who are contraindicated to MRI contrast agents (such as advanced renal failure or previous severe allergic reaction)
- Patients who cannot cooperate for MRI scanning.
- Patients show are unable to provide informed consent.

Consent form will be signed by patient before the examination. We currently aim to recruit approximately 50 patients for the purpose of the study according to the following basis for calculation of statistical power.

According to previous studies, there is an estimated ~60% predication of facial nerve with conventional techniques, and ~80% visualization of facial nerves using DESS. With 80% power and two-tail alpha of 0.05, at least 42 patients will be needed according to sample size calculation.

MRI scanning

Patient will be scheduled to be scanned at the Siemens Signa 3T MRI scanner at Gerald Choa Neuroscience Institute, the Chinese University of Hong Kong. The scanning protocol consists of conventional imaging sequences for salivary gland which includes the following sequences:

- Axial T1 weighted spin-echo
- Axial T2 weighted spin-echo (with fat saturation)
- Coronal T2 weighted spin-echo
- Diffusion-weighted imaging.
- Dynamic contrast-enhanced imaging of the salivary gland, with focus on the lesion.
- Axial post-contrast Axial T1 weighted spin-echo
- Axial post-contrast 3D T1-weighted fat-saturated SPACE

In addition, the following sequences will be performed for the purpose of facial nerve mapping:

- 3D Axial Dual-echo steady state sequence.
- Pre-contrast 3D Constructive interference in steady state
- Post-contrast 3D Constructive interference in steady state

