Contrast injection will be required for these patients as per usual salivary gland MRI protocol but no additional contrast administration is required for neurogram sequences as these can be performed concomitantly. The whole scanning protocol will take approximately 45 minutes.

Image interpretation

Images will be reviewed by two independent radiologists for the conspicuity of the facial nerves. The intra-parotid facial nerve will be segmented into eight segments, which includes the main trunk (distal to stylomastoid foramen), temporofacial division, cervicofacial division, and five branches (temporal branch, zygomatic, buccal, mandibular, cervical). For each branch, its conspicuity is measured objectively by ratio between the average signal intensity of the nerve as compared to the both the parotid parenchyma and the tumour on the respective sequence. Visual assessment of the nerve is also performed using a three point scale: 2. Whole intraparotid course of the concerned segment/ branch of facial nerve identified with certainty, 1. Partial visualization of the concerned segment/ branch of facial nerve, and 0. Particular branch cannot be identified. The process will be repeated on the DESS, post-contrast CISS and conventional **3D SPACE** sequences for bilateral facial nerves for each patient.

Inter-observer agreement between two observers are calculated using kappa statistics. The measured statistics of subjective and objective conspicuity are evaluated using statistics software (SPSS) using two-way comparison tests (Mann-Whitney U or two-smaples T test) as well as analysis of variance (ANOVA).

Handling and Storage of personal data

Images of usual salivary gland MRI sequences (excluding DESS and CISS sequences) will be uploaded to patient's electronic patient records for clinical use. The research sequences will be stored in the database only, except when the research sequences have impact on clinical management then selected images can be uploaded to ePR for illustration.

All MRI scans will be stored in the picture archiving and communication system of Gerald Choa Neuroscience Center/ Prince of Wales Hospital. These images can be viewed on HA clinical workstations for the purpose of providing clinical care. Radiologist with training in Head and Neck or Neuroradiology will issue a formal radiology report regarding in the examinations, the report will be available on the ePR system.

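### The signal ratio is measured per sequence with no common set of nerve segments, so if contrast drives visibility the comparison tilts against the sequence that shows more nerves

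*Protocol*

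**What the plan says.** All of the measurement rules are in the protocol, under Image interpretation.

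- **Unit.** "The intra-parotid facial nerve will be segmented into eight segments", on both sides of each patient.
- **Objective measure.** "its conspicuity is measured objectively by ratio between the average signal intensity of the nerve as compared to the both the parotid parenchyma and the" (the second reference is the tumour). Both references are read within the sequence concerned: "the parotid parenchyma and the tumour on the respective sequence". There are therefore two ratios per segment: nerve to parenchyma and nerve to tumour.
- **Visual measure.** A three-point score: 2 for the whole course seen, 1 for partial visualization, and at the bottom "0. Particular branch cannot be identified".
- **Repetition.** "The process will be repeated on the DESS, post-contrast CISS and conventional" 3D SPACE sequences.
- **Analysis.** Subjective and objective conspicuity go to Mann-Whitney U or two-sample t tests, and to ANOVA. No within-patient or within-segment form is mentioned.

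The section does not say what ratio, if any, a segment scored 0 receives. It describes no transfer of a nerve region from one sequence to another, and no restriction to segments seen on more than one sequence. Under Patient recruitment, the sample size rests on this statement: "there is an estimated ~60% predication of facial nerve with conventional techniques, and ~80% visualization of facial nerves using DESS".

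**The concern.** An average nerve signal needs a region drawn on the nerve. Where a sequence does not show the branch, the reader has nothing to draw on. Where it shows part of the branch, only that part can be measured. Followed as written, the rule yields ratios only for what each sequence already displays, and the sequences are expected to differ in exactly that respect.

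The ratio is named as a measure of conspicuity, which implies that nerves with more contrast are easier to see. The unmeasured segments are then mainly the faint ones. A sequence good enough to reveal faint branches adds low values to its own average, while a poorer sequence averages only its easy nerves. The ratio comparison could then understate a real advantage, or disagree with the visual score for no anatomical reason. Recruiting more patients would not change this, because the bias does not depend on sample size.

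**Working it through.** **Inputs from the protocol.** 8 segments per side on two sides, so 16 per patient per sequence; about 50 patients; planning rates of 60% (conventional) and 80% (DESS); 80% power; two-sided alpha 0.05; stated minimum 42.

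**The plan's own figure.** The one-sample proportion formula reproduces it:

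n = [(1.960 × √(0.60 × 0.40) + 0.842 × √(0.80 × 0.20)) / 0.20]² = 42.04.

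This shows that the two rates are the planning contrast. The figure of 42 itself does not bear on the point.

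**How far the sets could differ.** Assume the rates apply per segment.

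- 50 × 16 = 800 segments per sequence, so about 0.60 × 800 = 480 are measurable on conventional imaging and 0.80 × 800 = 640 on DESS.
- The share seen on both lies between 0.60 + 0.80 - 1 = 40% and 60%, that is 320 to 480 segments.
- The share contributing to one sequence only is 0.60 + 0.80 - 2 × (share on both), that is 20% to 60%.

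**Bias when true contrast is equal.** Further assumptions: contrast is standard normal on each sequence, signed so that larger means the nerve stands out more, and visibility is a threshold on a latent variable with correlation r to contrast. For a fraction p seen with threshold t, the mean contrast among seen segments is r × φ(t)/p.

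- Conventional: t = -0.253, φ = 0.3863, so 0.3863/0.60 = 0.644 at r = 1.
- DESS: t = -0.842, φ = 0.2800, so 0.2800/0.80 = 0.350 at r = 1.
- Bias = r × (0.350 - 0.644) = -0.294 r.

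| Correlation r of visibility with the ratio | Bias, DESS minus conventional (SD) |
|---|---|
| 0 | 0 |
| 0.3 | -0.09 |
| 0.5 | -0.15 |
| 0.7 | -0.21 |
| 1 | -0.29 |

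**Bias when DESS truly has more contrast.** Take r = 1 and one common threshold of 0. Means of 0.842 and 0.253 give 80% and 60% seen, with a true difference of 0.588. The means among seen segments are 0.842 + 0.350 = 1.192 and 0.253 + 0.644 = 0.897. The observed difference is 0.294, half the true one. With different thresholds, still at r = 1, a true advantage of 1.0 SD appears as 0.71 and one of 0.2 SD as -0.09. A large advantage is shrunk; only a small one can change sign.

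**Candidate remedies.** Simulation of 2 million segments, equal true contrast, r = 1 (the worst case), by between-sequence correlation of contrast:

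| Set compared | 0.5 | 0.7 | 0.9 |
|---|---|---|---|
| Each sequence's own seen segments | -0.29 | -0.29 | -0.29 |
| Segments seen on both | -0.18 | -0.12 | -0.05 |
| Segments seen on either, region copied without error | +0.05 | +0.04 | +0.03 |

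The last row assumes perfect registration. In this model 26% to 30% of that set is copied onto the poorer sequence and only 1% to 7% onto the better one, so copying loss is asymmetric. Suppose copied regions lose 30% of their contrast and mean contrast lies 1.5 to 2 SD above none. The result is then about +0.09 to +0.14 SD in favour of the better sequence; at 50% loss it is about +0.13 to +0.20 SD. The loss and the mean contrast are assumptions; the protocol gives neither.

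**The case against.** The strongest reply is that the restriction to visible nerve is an inference. The protocol asks for a ratio for each branch. It does not forbid placing a region by anatomy or from another sequence, and the handling of unmeasurable segments could sit in an analysis plan or reading manual that is not shown. Part of this stands: the text is silent, not explicit. But where and how the ratio is taken is a reading rule that this section does fix, on the respective sequence, next to a scale whose lowest level means "Particular branch cannot be identified". The rule has to be settled before regions are drawn, because a later analysis plan cannot recover values that were never measured.

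Four stronger readings are tempting, and the documents do not support them.

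- **That 40% of segments on conventional imaging and 20% on DESS will have no ratio.** The planning sentence gives no unit (segment, nerve or patient), does not equate conventional techniques with 3D SPACE, and does not tie either rate to score 0. If the rates mean full visualization, segments scored 1 still yield a ratio and fewer are missing.
- **That the bias is 0.29 SD.** That is the extreme in which the ratio alone decides visibility. If calibre or resolution decides it, the bias may be small or nil.
- **That both ratios suffer alike.** A branch lying away from the tumour need not be seen or missed according to its nerve-to-tumour ratio, so the model fits the parenchyma ratio better. Equal spread on every sequence is also assumed.
- **That half of the trial's evidence is compromised.** The protocol gives the ratio no such weight. The sample size rests on visualization rates, and the visual score keeps unseen branches as 0.

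**Conclusion.** The point holds in a limited form. As written, the objective comparison draws each sequence's ratios from a different set of segments, and nothing in the stated tests restores a common one. That follows from the text.

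The direction, against the sequence showing more nerves, is conditional on visibility rising with contrast. The word conspicuity implies this, but the protocol does not demonstrate it. The size is not known from the documents: 0 to -0.29 SD, with about -0.15 SD at a correlation of 0.5, given normal contrast and the 60% and 80% rates applied per segment. No visualization rate is given for CISS, so nothing can be computed for it.

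**What to change.** Before regions are drawn, amend Image interpretation as follows.

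1. **Main ratio comparison.** Compare within patient and segment, on segments scored 1 or 2 on both sequences of each pair.
2. **Reporting.** Give the number of unmeasurable segments per sequence.
3. **Sensitivity analysis.** Once the visual scores are locked, take each segment seen on at least one sequence, copy its region by co-registration to the same position on the others, and measure all three.

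Read the two results side by side as bounds. The common set still leans against the better sequence, by about -0.05 to -0.18 SD in the worst case at between-sequence correlations of 0.9 to 0.5. Copied regions may lean the other way, because registration error on thin nerves lowers the copied ratios mainly on the poorer sequence.

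The cost is protocol wording, extra region work on images already acquired, and fewer segments in the paired comparison. No further scans or patients are needed.

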Scientific title

Application of 3D magnetic resonance neurogram sequences for evaluation of Intraparotid facial nerves in patients with parotid neoplasm

Research protocol

Version 4

Date: 6 June 2022

NCT number: NCT05296109

Scientific basis

Parotid neoplasm consists of a wide range of benign and malignant lesions, and parotidectomy has been the mainstay for management of these neoplasms. Within the parotid gland there are branches of the intra-parotid facial nerves, which are tiny in calibre and are prone to injury during operation. It has been reported in recent retrospective reviews that the incidence of temporary and permanent facial nerve injury were 9.2% and 5.2% respectively, the risk of which increased with old age, malignant tumour and revision surgery [1]. Traditionally the incident of facial nerve injury is reduced by intra-operative facial nerve monitoring and surgical magnification, while imaging has limited role in aiding this purpose.

MRI is considered a cornerstone modality in the diagnosis and management of salivary gland tumours, with multi-parametric imaging providing clue to the underlying histology and relationship with adjacent structures. With the advancement of MRI, new and higher resolution three-dimensional sequences such as Dual echo Steady State (DESS) or constructive interference in steady state (CISS) sequences have been shown to better demonstrate the extracranial, intraparotid facial nerves [2-3]. More recent studies have also shown potential use of delineation of facial nerve branches in relationship to tumour [4]. However, the advantages and disadvantages of these sequences remain unknown. Our study aim to compare the efficacy between the two sequences, and also to compare with conventional 3D post-contrast anatomical imaging studies in the localization and visualization of the facial nerve branches in patients with tumour.

Reference:

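### Independent-groups tests (Mann-Whitney U, two-sample t) are named for comparing MRI sequences that are all read on the same nerves of the same patients

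*Protocol*

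**What the plan says.** The Scientific basis section gives the aim: "Our study aim to compare the efficacy between the two sequences, and also to compare with conventional 3D post-contrast anatomical imaging studies". The Study protocol section describes a single "prospective cohort model comparing between the efficacy of different MRI sequences in visualization of the facial nerves", so what is compared is sequences, not groups of patients.

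Under Image interpretation, "The intra-parotid facial nerve will be segmented into eight segments", and each segment receives signal-intensity ratios and a visual score of 0, 1 or 2. The reading is then repeated within the patient: "The process will be repeated on the DESS, post-contrast CISS and conventional" 3D SPACE "sequences for bilateral facial nerves for each patient".

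The next paragraph of that section names the analysis of both measures: "two-way comparison tests (Mann-Whitney U or two-smaples T test"), "as well as analysis of variance (ANOVA"). The form of the ANOVA is not given. No paired, repeated-measures or clustered method is mentioned.

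**The concern.** Mann-Whitney U and the two-sample t test take the standard error of a difference as if the two sets of values came from unrelated subjects. Here each patient supplies a value under every sequence, from the same nerve, around the same tumour and by the same readers. Some patients' nerves will be easy to see on every sequence and others hard on every sequence. A within-patient analysis removes that variation, whereas the named tests leave it in the error term.

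The protocol describes no separate-group comparison that these tests could serve. Even a contrast of the two sides of the face would be within-patient.

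The central result of the study, which sequence shows the nerve better, would therefore rest on tests whose error rates are not those claimed. Depending on how the rows are laid out, a real difference could be missed or a false one reported, and a reader could not tell which.

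**Working it through.** **Inputs from the protocol.** Target of about 50 patients, minimum 42, rates of about 60% (conventional) and 80% (DESS), 80% power, two-sided alpha 0.05 (Patient recruitment). Eight segments per nerve on two sides, so 8 × 2 = 16 segment values per patient per sequence (Image interpretation).

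**Inputs assumed.** The protocol gives no correlation between sequences, no SD-scaled difference and no variance shares. All of these are assumptions, shown as ranges.

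**The protocol's own figure.** A one-sample calculation, null 0.60 against 0.80, gives [1.96·√(0.6·0.4) + 0.8416·√(0.8·0.2)]² / 0.2² = 42.04, matching the stated 42. A two-sample comparison of proportions would need 82 per group. A paired McNemar calculation gives 42 only if about 22.6% of pairs are discordant. The basis of the 42 is a separate matter, and no shortfall from the planned 80% power is attributed here to the choice of test.

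**Case 1: signal-intensity ratio, one value per patient.** Let r be the correlation between two sequences, d the shift in SD units and n = 50. The unpaired statistic is approximately N(d·√(n/2), 1 − r), not N(d·√(n/2), 1). Hence:

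- true type I error = 2·[1 − Φ(1.96/√(1 − r))]; at r = 0.3 this is 2·[1 − Φ(2.343)] = 1.9%;
- with d = 0.4, d·√(n/2) = 0.4 × 5 = 2.0. At r = 0.3, unpaired power ≈ Φ((2.0 − 1.96)/√0.7) = 52% and paired power ≈ Φ(2.0/√0.7 − 1.96) = 67%. Using t rather than normal distributions (simulation with 40,000 replicates; noncentral t for the paired test) gives 51% and 65%.

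| r | two-sample t: type I error | two-sample t: power | paired t: power |
|---|---|---|---|
| 0 | 5% | 51% | 50% |
| 0.1 | 3.9% | 51% | 54% |
| 0.2 | 2.8% | 51% | 59% |
| 0.3 | 1.9% | 51% | 65% |
| 0.5 | 0.6% | 51% | 79% |

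The shift detectable with 80% power at r = 0, 0.3 and 0.5 is 0.57, 0.54 and 0.52 SD for the two-sample t test, against 0.57, 0.48 and 0.40 SD for the paired t test.

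**Case 2: visual score, same 0.4 SD shift on a latent scale.** The latent scale is cut into equal thirds, with one score per patient (10,000 replicates). This is a stylised version of the planned data.

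| latent r | Mann-Whitney: type I error | Mann-Whitney: power | signed-rank: power |
|---|---|---|---|
| 0 | 4.8% | 43% | 42% |
| 0.3 | 2.5% | 41% | 51% |
| 0.5 | 1.2% | 40% | 61% |

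**Case 3: k segment values per patient entered as independent rows.** Split a total variance of 1 into a patient share vp, a patient-by-sequence share vi, a segment share common to the sequences vs, and the remainder. The true variance of the difference in means, divided by the variance the test assumes, is

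ratio = (1 − vp − vi − vs) + k·vi, and type I error = 2·[1 − Φ(1.96/√ratio)].

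For k = 16, vp = 20%, vi = 5%, vs = 0: ratio = 0.75 + 0.80 = 1.55, so type I error = 2·[1 − Φ(1.574)] ≈ 12%. With vp = 40%: ratio = 0.55 + 0.80 = 1.35, giving about 9%. Over vp = 20–40%:

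| rows per patient | vs | vi = 0 | vi = 5% | vi = 10% |
|---|---|---|---|---|
| 16 | 0 | 1–3% | 9–12% | 18–20% |
| 16 | 30% | below 1% | 6–8% | 14–17% |
| 8 (one side) | 0 | – | 4–7% | 9–11% |
| 8 (one side) | 30% | – | 2–3% | 5–7% |

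Simulation of the 16-row case (3,000 replicates, vp = 20% and 40%) gave 11.2% and 9.4% at vi = 5%, and 18.3% and 17.8% at vi = 10%, with vs = 0. With vs = 30% it gave 8.4% and 6.7%, then 16.9% and 13.7%. A separate simulation with other variance splits (2,000 replicates) put the pooled t test and Mann-Whitney at about 1%, 8–9%, 16% and 28–31% for vi = 0, 5%, 10% and 20%. A paired t test on patient means stayed at about 4–6% throughout.

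**The case against.** The strongest reply has four parts.

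- **ANOVA is also named.** Run as a repeated-measures analysis, it would be valid for the three sequences. That stands: for ANOVA the remedy is to state its form. It does not rescue the pairwise tests, which the protocol names explicitly in their unpaired versions.
- **The size and direction of the error are not known.** At zero correlation with one value per patient the tests are correct, and some pooled settings fall close to 5%. In the most natural reading, positive correlation and one value per patient, the tests are conservative, so a significant result stands and only power is lost. Inflation needs two further conditions that the protocol does not state: segments entered as independent rows, and sequence effects that differ between patients. All of this stands and limits the claim to a nominal level that is not assured.
- **The calculations simplify the data.** No single 0/1/2 score per patient exists as planned, equal thirds are not tied to the 60% and 80% rates, and a nerve-to-tumour ratio would ordinarily exist only on the tumour side. The 8-row figures cover that last point. The rest means the percentages show direction and order of size, not predictions.
- **Pairing alone is not a complete plan.** A segment that cannot be identified has no measurable ratio, so per-patient means may average different segments on different sequences, and two readers' values must be combined somehow. This bears on how the fix is written. A mixed model or GEE can take unequal numbers of segments per patient.

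The point cannot be set aside as a detail left to an analysis plan that is not shown. The protocol states the tests, and a later document naming paired tests would contradict it.

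**Conclusion.** The concern holds. The pairwise tests named in the protocol do not fit its within-patient design, and no other comparison is described for which they would.

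With one value per patient and an assumed positive correlation, the tests are conservative. At 50 patients and an assumed correlation of 0.3 to 0.5, the two-sample t test runs at 1.9% to 0.6% instead of 5%. It has 51% power for an assumed 0.4 SD shift where a paired t test has 65% to 79%. With all 16 segment values entered as independent rows, type I error ranges from below 1% to about 20% as the assumed patient-by-sequence share goes from 0 to 10%.

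What does not depend on these assumptions is that the tests ignore the pairing, so the 5% level is not assured and its direction cannot be read from the protocol. This should be corrected before analysis. It affects neither the scanning nor the data collected.

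**What to change.** In the Image interpretation section, replace the Mann-Whitney U and two-sample t tests with within-patient methods:

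- **Per-patient summary:** Wilcoxon signed-rank or paired t test for each pair of sequences, and Friedman or repeated-measures ANOVA for all three. State that the ANOVA already named is the repeated-measures form.
- **Segments and sides analysed together:** a linear mixed model (ratio) or ordinal mixed model (0/1/2 score), or GEE, with sequence as a within-patient factor and patient as the cluster, allowing the sequence effect to vary between patients.

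The same sentence should say how the two readers' values are combined and how segments with no measurable ratio are handled, since both affect what is paired with what.

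The cost is a change of analysis wording, possible at any time before analysis. The methods are standard, and no further patients, scans or readings are needed.

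### Three sequences are compared pairwise and by ANOVA on three measures with no primary comparison or endpoint, while the only alpha and the sample size belong to one contrast

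*Protocol*

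**What the plan says.** All references are to the protocol; the statistical analysis plan is not at hand.

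- **Scientific basis.** The aim is to compare DESS with CISS and also to compare them with conventional 3D post-contrast imaging. DESS v CISS comes first in the sentence, but nothing is ranked.
- **Patient recruitment (sample size).** The assumptions are that "there is an estimated ~60% predication of facial nerve with conventional techniques" and that there is about "80% visualization of facial nerves using DESS". From these: "With 80% power and two-tail alpha of 0.05, at least 42 patients will be needed according to sample size calculation". The recruitment target is set a little higher: "We currently aim to recruit approximately 50 patients". This is the only place where an alpha appears.
- **Image interpretation.** "The intra-parotid facial nerve will be segmented into eight segments". Each branch has an objective measure, the "ratio between the average signal intensity of the nerve as compared to the both the parotid parenchyma and the tumour", which makes two ratios, and a visual score of 0, 1 or 2. "The process will be repeated on the DESS, post-contrast CISS and conventional" 3D SPACE sequences, on both sides. The analysis uses "two-way comparison tests (Mann-Whitney U or two-smaples T test) as well as analysis of variance (ANOVA".

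No comparison, measure or segment is called primary. No order is given between the ANOVA and the pairwise tests.

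**The concern.** The design claim (two-tailed 0.05, 80% power) is made for a single contrast on a single proportion. The analysis text describes three pairs of sequences and three measures, and does not say which result carries that claim.

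The sized contrast also cannot be matched to a planned test. The sample size uses a proportion visualised. The analysis text does not define one: it does not say whether a score of 1 counts as visualised, or whether the unit is the segment, the side or the patient.

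Two things are at stake. A favourable result on any pair or measure could be presented as the trial's answer at 0.05, although the chance of some such result under no difference may be well above 0.05. And if the visual score and the signal ratios disagree, nothing says which one answers the aim.

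**Working it through.** **Reproducing the stated 42.** Inputs from the sample-size paragraph: p0 = 0.60, p1 = 0.80, two-tailed alpha 0.05, power 80%. A one-sample test of a proportion against a fixed 60% gives

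n = (1.960·√0.24 + 0.8416·√0.16)² / 0.20² = (0.9602 + 0.3366)² / 0.04 = 42.04.

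This agrees with 42 and is one contrast at one alpha. On the same formula, 50 patients give 87% power.

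**Counting the tests.** Three sequences make 3 pairs. Three measures make 3 × 3 = 9 tests if segments are pooled. Testing each of eight segments separately would make 9 × 8 = 72, but the protocol does not say that this is done.

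**Familywise error if each test is read at 0.05.** For k independent tests it is 1 − 0.95^k: 14.3% for 3, 37.0% for 9 and 97.5% for 72.

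The tests are not independent, so the error was also simulated with 50 patients, three equal sequences and normal data. The correlation between sequences within a patient was set at 0 to 0.7, and that between measures (and segments) at 0 to 0.5. All these correlations are assumptions.

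| Tests | Correlation between sequences | 3 pairs, one measure | 9 tests | 72 tests (inferred) |
|---|---|---|---|---|
| Paired t | 0 to 0.7 | 12–14% | 28–33% | 78–96% |
| Two-sample t, as named | 0.3 | about 5% | 12–15% | 46–71% |
| Two-sample t, as named | 0.5 | about 1–2% | about 5% | 22–33% |
| Two-sample t, as named | 0.7 | below 1% | below 1% | 4–5% |

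The unpaired rows are lower because all three sequences come from the same patients. An unpaired test ignores that correlation and rejects too seldom: about 2% of the time for a single test at correlation 0.3.

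**What the choice does to the sample size.** On the formula that reproduces 42:

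- One primary comparison at 0.05: n = 42; power 80% at 42 patients, 87% at 50.
- Three pairs sharing alpha by Bonferroni (0.05/3 = 0.0167, z = 2.394): n = (2.394·0.4899 + 0.3366)² / 0.04 = 57; power 62% at 42, 73% at 50.
- Nine tests (0.05/9 = 0.0056): n = 72; power 44% at 42, 56% at 50.

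**Hierarchies.** Simulation with 50 patients, three equal sequences and paired tests:

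- Three ungated pairs: 12.6%.
- All three pairs behind a repeated-measures omnibus test: 5.0%.
- Primary tested regardless, with only the other two behind the omnibus test: 7.7%.
- Primary first, others only if it is significant: about 5%.

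**The case against.** **No per-test level is stated.** A reader might infer that every pairwise test is run at 0.05. The protocol gives 0.05 only in the sample-size sentence. If the sized contrast alone is tested at that level, its alpha is held. This stands.

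**Per-segment testing is an inference.** Eight segments are the unit of measurement. The analysis sentence does not say that they are tested separately, and scores could be pooled. The 72-test figures, and the 72 × 0.05 = 3.6 false positives expected under no difference, are therefore an upper scenario.

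**A false claim is not shown to be very probable.** That stronger reading is tempting from the paired figures, but the tests named are unpaired and conservative on same-patient data. The documents give no correlation between sequences, and at 0.5 or more the three-pair and nine-test errors are about 5% or less. This stands. It is a weak defence, though: the protection comes from a mismatched test, costs power and disappears once a paired test is used.

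**The wording does not exclude an omnibus gate.** Listing ANOVA beside the pairwise tests fixes no order. An omnibus test first would be compatible with the text, but is not stated.

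**Correction rules belong in the analysis plan.** Agreed: the absence of a multiplicity procedure is no finding here. What remains is narrower. Which comparison and endpoint carry the stated alpha and power is a protocol-level choice. The protocol sizes on one contrast, lists another first in its aim and ranks none in its analysis.

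**Conclusion.** The point holds in limited form. The protocol plans pairwise tests and ANOVA for three sequences on three measures without naming a primary comparison or endpoint, while its alpha and sample size refer only to DESS v conventional.

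An overall 0.05 is then not assured. The size of the excess is conditional on all tests being read at 0.05. It is about 12 to 14% for three pairs and 28 to 37% for nine tests if valid paired tests are used. With the unpaired tests named, there may be little or none, depending on a within-patient correlation that the documents do not give.

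The 80% power claim depends on the same unmade choice: 42 patients suffice on the plan's own formula for one comparison at 0.05, and 57 are needed if three pairs share the alpha. The point should be settled before analysis, and wording is enough to settle the hierarchy.

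**What to change.** In Image interpretation:

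1. Name DESS v 3D SPACE as the primary comparison at two-sided 0.05. It is the contrast that the sample size is built on.
2. Define the primary endpoint from the visual score so that it matches the 60%/80% assumption. State which scores count as visualised and the unit of analysis (segment, side or patient). Use a paired test that respects that unit.
3. State a hierarchy for the other two pairs. The simplest is a fixed sequence in which each is tested only if the previous comparison is significant. The order is for the sponsor, since the aim lists DESS v CISS first. If the sponsor wants that pair as primary, the 60%/80% basis no longer applies and the sample size needs its own assumption.
4. If a three-sequence omnibus test is preferred, put all three pairs behind it. Leaving the primary outside while the others depend only on the omnibus test gives about 7.7%.
5. Label the signal ratios and per-segment results secondary or descriptive, with confidence intervals.

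**Cost.** Protocol wording and fewer confirmatory claims. In a fixed sequence the primary comparison loses no power. If the omnibus test also gates the primary, a pairwise test with 80% power falls to about 70 to 76%.

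**Check to make with it.** The 42 comes from a one-sample formula. For one paired yes/no result per patient, the McNemar formula is n = (1.960·√pd + 0.8416·√(pd − 0.04))² / 0.04, with pd = 0.20 + 2q. Here q is the share seen on conventional imaging but not on DESS. It gives 37 patients at q = 0, 50 at about q = 0.033 and 84 at q = 0.12. The protocol gives no q, so the sponsor should state one and confirm that 50 is enough.
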